4.4 Diet/Activity/Other Considerations

4.4.1 Diet

Subjects should maintain a normal diet unless modifications are required to manage an AE such as diarrhea, nausea or vomiting.

4.4.2 Contraception

Pembrolizumab may have adverse effects on a fetus in utero. Furthermore, it is not known if pembrolizumab has transient adverse effects on the composition of sperm.

For this trial, male subjects will be considered to be of non-reproductive potential if they have azoospermia (whether due to having had a vasectomy or due to an underlying medical condition).

Female subjects will be considered of non-reproductive potential if they are either:

(1) postmenopausal (defined as at least 12 months with no menses without an alternative medical cause; in women < 45 years of age a high follicle stimulating hormone (FSH) level in the postmenopausal range may be used to confirm a post-menopausal state in women not using hormonal contraception or hormonal replacement therapy. In the absence of 12 months of amenorrhea, a single FSH measurement is insufficient.);

OR

(2) have had a hysterectomy and/or bilateral oophorectomy, bilateral salpingectomy or bilateral tubal ligation/occlusion, at least 6 weeks prior to screening;

OR

(3) has a congenital or acquired condition that prevents childbearing.

Female and male subjects of reproductive potential must agree to avoid becoming pregnant or impregnating a partner, respectively, while receiving study drug and until at least 12 months after the last dose of study therapy by complying with one of the following:

(1) practice abstinence[†] from heterosexual activity;

OR

(2) use (or have their partner use) acceptable contraception during heterosexual activity.

Acceptable methods of contraception are[‡]:

Single method (one of the following is acceptable):

• intrauterine device (IUD)

Protocol v4.0 dated 21 July 2021

- vasectomy of a female subject's male partner
- contraceptive rod implanted into the skin

Combination method (requires use of two of the following):

- diaphragm with spermicide (cannot be used in conjunction with cervical cap/spermicide)
- cervical cap with spermicide (nulliparous women only)
- contraceptive sponge (nulliparous women only)
- male condom or female condom (cannot be used together)
- hormonal contraceptive: oral contraceptive pill (estrogen/progestin-only pill), contraceptive skin patch, vaginal contraceptive ring, or subcutaneous contraceptive injection

[†]Abstinence (relative to heterosexual activity) can be used as the sole method of contraception if it is consistently employed as the subject's preferred and usual lifestyle and if considered acceptable by local regulatory agencies and ERCs/IRBs. Periodic abstinence (e.g., calendar, ovulation, sympto-thermal, post-ovulation methods, etc.) and withdrawal are not acceptable methods of contraception.

‡If a contraceptive method listed above is restricted by local regulations/guidelines, then it does not qualify as an acceptable method of contraception for subjects participating at sites in this country/region.

Subjects should be informed that taking the study medication may involve unknown risks to the fetus (unborn baby) if pregnancy were to occur during the study. In order to participate in the study, subjects of childbearing potential must adhere to the contraception requirement (described above) from the day of study medication initiation (or 14 days prior to the initiation of study medication for oral contraception) throughout the study period until at least 12 months after the last dose of study therapy. If there is any question that a subject of childbearing potential will not reliably comply with the requirements for contraception, that subject should not be entered into the study.

4.4.3 Use in Pregnancy

If a subject inadvertently becomes pregnant while on treatment with pembrolizumab, the subject will immediately be removed from the study. The site will contact the subject at least monthly and document the subject's status until the pregnancy has been completed or terminated. The outcome of the pregnancy will be reported to within 2 working days to Merck if the outcome is a serious adverse event (e.g., death, abortion, congenital anomaly, or other disabling or life-threatening complication to the mother or newborn).

The Sponsor-investigator will make every effort to obtain permission to follow the outcome of the pregnancy and report the condition of the fetus or newborn to Merck. If a male subject impregnates his female partner the study personnel at the site must be informed immediately and the pregnancy reported to Merck.

4.4.4 Use in Nursing Women

It is unknown whether pembrolizumab is excreted in human milk. Since many drugs are excreted in human milk, and because of the potential for serious adverse reactions in the nursing infant, subjects who are breast-feeding are not eligible for enrollment.

4.5 Subject Withdrawal/Discontinuation Criteria

Subjects may withdraw consent at any time for any reason or be discontinued from the trial at the discretion of the investigator should any untoward effect occur. In addition, a subject may be withdrawn by the investigator if enrollment into the trial is inappropriate, the trial plan is violated, or for administrative and/or other safety reasons. Specific details regarding discontinuation or withdrawal are provided in Section 6.1.3.1.

A subject must be discontinued from the trial for any of the following reasons:

- The subject or legal representative (such as a parent or legal guardian) withdraws consent.
- Confirmed radiographic disease progression

Note: For unconfirmed radiographic disease progression, patients may remain on study until progression is confirmed by repeat imaging or biopsy.

- Unacceptable adverse experiences as described in Section 6.2
- Intercurrent illness that prevents further administration of treatment
- Investigator's decision to withdraw the subject
- The subject has a confirmed positive serum pregnancy test
- Noncompliance with trial treatment or procedure requirements
- The subject is lost to follow-up
- Completed trial therapy, including Retreatment if applicable (see section 6.1.4.2, Treatment Period)
- Administrative reasons

Study visits are listed in Section 5 (Trial Flow Chart) and Section 6.1.4 (Visit Requirements). After the last cycle of pembrolizumab, each subject will be followed for 90 days for adverse event monitoring and will have an Off-Study visit at that time. Patients who discontinue for reasons other than progressive disease will have post-treatment follow-up as per standard of care, including disease status and survival.

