2.2 Secondary Objectives

(1) To evaluate the safety and tolerability of the combination of CD20-directed therapy and pembrolizumab

(2) To evaluate 2-year progression-free survival (PFS) and overall survival (OS) in each treatment group

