5.0 TRIAL FLOW CHART

5.1 Study Flow Chart

Trial Period:	Screening Phase	Treatment – Induction (cycles 1-4)					Treatment – Extended therapy (cycles 5, up to 35 max)	Off-Study Visit
Treatment Cycle/Title:	Study Screening	Cycle 1 day 1	Cycle 1 day 8	Cycle 1 day 15	Cycle 2 day 1	Cycle 3-4 day 1	Cycles 5-35, day 1	90 days after last dose of pembrolizumab
Scheduling Window (Days):	-42 to -1	± 3	± 3	± 3	± 3	± 3	± 5	+/- 7
Administrative Procedures								
Informed Consent	Х							
Inclusion/Exclusion Criteria	Х							
Medical History	Х	\mathbf{X}^1			X	X	Х	Х
Prior and Concomitant Medication Review	Х	\mathbf{X}^1			X	X	Х	Х
Arm A & B: Rituximab Administration		Х	Х	X	Х			
Arm A, B & C: Pembrolizumab Administration		Х			X	X	Х	
Arm C: Obinutuzumab administration		Х	X	X	X		(Cycles 5,9,13,17,21,25 only)	
Post-study anticancer therapy status								Х

Survival Status								х
Clinical Procedures/Assessment	s				1	1	1	
Review Adverse Events	X (baseline AE)	\mathbf{X}^1			X	X	X	Х
Full Physical Examination	Х							Х
Directed Physical Examination		X^1			X	Х	Х	
Vital Signs and Weight (Height at Screening)	Х	\mathbf{X}^1			X	X	X	Х
ECOG Performance Status	Х	\mathbf{X}^1			x	X	x	Х
Laboratory Procedures/Assessm	ients: analysis perfo	ormed by L	OCAL	laborator	y	1		
Pregnancy Test – Urine or Serum β-HCG	X ⁶							
PT/INR and aPTT	Х							
CBC with Differential	Х	X^1			X	Х	Х	Х
Comprehensive Chemistry Panel, LDH	Х	\mathbf{X}^1			X	X	X	Х
Urinalysis	Х							
T3, FT4 and TSH	Х				X	Х	Х	Х
HepB S Ag, Hep B Core Ab, Hep C Ab	Х							
Efficacy Measurements								
Tumor Imaging	X ²						X- within 2 weeks before starting Cycle 5 and Cycle 9, then q 4 cycles (q 3 mo) ²	
Bone marrow aspirate	X ⁵							
Tumor Biopsies/Archival Tissue Collection/Correlative Studies Blood								
Archival or Newly Obtained	X ³	X ³	X ³	X ³	X ³			

Tissue Collection								
Correlative Studies Blood Collection	X ⁴						X ⁴	X4
1. Medical history, AE review, Prior/Concomitant medication review, weight, and ECOG, PE, height/weight, and lab studies do not need to be repeated if done within 7 days of start cycle 1 day 1 (e.g. at screening visit). VS should be recorded at screening and at each treatment visit.								

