6.1.6.3 Off-Study Visit

The mandatory Off-Study Visit should be conducted approximately 90 days (+/- 7days) after the last dose of pembrolizumab irrespective of reason it was stopped, but may be done earlier for patients embarking on additional anti-lymphoma therapy. All AEs that occur prior to the Off-Study Visit should be recorded. Subjects with an AE of Grade > 1 will be followed until stabilization or resolution of the AE to Grade 0-1 or until the beginning of a new anti-neoplastic therapy, whichever occurs first. SAEs that occur within 90 days of the end of treatment or before initiation of a new anti-cancer treatment should also be followed and recorded.

The off-study visit will include laboratory studies (CBC diff, CMP, LDH), medical history, physical exam, remission status, concomitant medications, adverse events, and documentation of any ECI and subsequent management.

After the off-study visit, additional surveillance will be conducted as per routine standard of care. Every effort should be made to collect information regarding disease status until the start of new anti-neoplastic therapy, disease progression, death, or end of study. Information regarding post-study anti-neoplastic treatment will be collected if new treatment is initiated.

Patients who initiated retreatment require a second off-study visit, to be performed as above 90 days after their last dose of pembrolizumab (+/-7 days).

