6.5 Reporting Requirements for Adverse Events/Adverse Reactions

6.6 Serious Adverse Events

A serious adverse event is any adverse event occurring at any dose or during any use of Merck's product that:

- Results in death;
- Is life threatening;
- Results in persistent or significant disability/incapacity;
- Results in or prolongs an existing inpatient hospitalization;
- Is a congenital anomaly/birth defect;
- Is a new cancer (that is not a condition of the study);
- Is associated with an overdose;
- Is another important medical event

Exceptions to Serious Adverse Event Reporting include events related to progression of the cancer under study, including hospitalization or death. These events are not to be reported as serious adverse events. Hospitalization related to convenience (e.g. transportation issues, etc.) will not be considered an SAE. Any serious adverse event, or follow up to a serious adverse event, including death due to any cause other than progression of the cancer under study that occurs to any subject from the time the consent is signed through 90 days following cessation of treatment, or the initiation of new anti-cancer therapy, whichever is earlier, whether or not related to Merck product, must be reported within 2 business days of investigator knowledge to Merck Global Safety.

Additionally, any serious adverse event, considered by an investigator who is a qualified physician to be related to Merck product that is brought to the attention of the investigator at any time outside of the time period specified in the previous paragraph also must be reported immediately to Merck.

SAE reports and any other relevant safety information are to be forwarded to the Merck Global Safety [contact]

A copy of all 15 Day Reports and Annual Progress Reports is submitted as required by FDA, European Union (EU), Pharmaceutical and Medical Devices agency (PMDA) or other local regulators. Investigators will cross reference this submission according to local regulations to the Merck Investigational Compound Number (IND, CSA, etc.) at the time of submission. Additionally investigators will submit a copy of these reports to Merck & Co., Inc. (Attn: Worldwide Product Safety; [contact]) at the time of submission to FDA.

All subjects with serious adverse events must be followed up for outcome.

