7.0 STATISTICAL ANALYSIS PLAN

This study administers therapy to two groups of patients, relapsed/refractory FL and relapsed/refractory DLBCL.

Subjects who fail to complete study therapy or withdraw consent before the first response assessment for reasons other than disease progression, death, SAE, or drug-related adverse events will be replaced, to allow response assessment in accordance with study stopping rules. The first group (Arm A) includes patients with relapsed or refractory follicular lymphoma, and will include at least 9 patients with rituximab-refractory disease.

The second group (Arm B) consists of patients with relapsed/refractory diffuse large B-cell lymphoma ineligible for, or failing to respond to or progressing, after autologous stem cell transplantation.

These groups will employ independent rules, using Simon's two-stage design, and accrual will be suspended for review if futility thresholds are met. Two-stage designs which limit the maximum sample size will be considered. Once enrollment is suspended, the nature of events to leading to stopping will be assessed by the Principal Investigator and reported to institutional regulatory authorities, in accordance with the institutional Data Safety Monitoring Plan. The institutional Data Safety Monitoring Committee will determine whether any further accrual may proceed. Statistical analysis will entail descriptive statistics. Categorical variables will be summarized by number and percentage, and continuous variables will be summarized by min/median/max/mean/sd, respectively. Overall response rate, and response quality, will be evaluated according to CT criteria and PET/CT in relevant patients, as per the 2014 Lugano criteria.²⁸ PFS/OS distribution will be estimated and Kaplan-Meier curves will be presented. Log-rank testing and Cox proportional hazard regression models might be applied to evaluate the association between survival endpoints and prognostic factors. To compare continuous variable in the correlative studies, student's t-test and regression analysis might be applied if deemed appropriate.

Subjects who fail to complete study therapy before the first response assessment for reasons other than disease progression, death, SAE, or drug-related adverse events will be replaced, to allow response assessment in accordance with study stopping rules.

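### No survival follow-up is required after the Off-Study visit for patients who stop because of progression, so Kaplan-Meier 2-year OS is biased upward if they are censored at last contact

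*Combined protocol and SAP*

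**What the plan says.** Section 2.2 lists as a secondary objective: "To evaluate 2-year progression-free survival (PFS) and overall survival (OS) in each treatment group". For the analysis, Section 7.0 says "PFS/OS distribution will be estimated and Kaplan-Meier curves will be presented". It does not define OS or say when a patient is censored for it.

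Section 4.5 governs what happens after treatment. Under the words "A subject must be discontinued from the trial for any of the following reasons" it lists confirmed radiographic progression. It then says that after the last pembrolizumab cycle "each subject will be followed for 90 days for adverse event monitoring and will have an Off-Study visit at that time". Follow-up beyond that point is given to one group: "Patients who discontinue for reasons other than progressive disease will have post-treatment follow-up as per standard of care, including disease status and survival".

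Three other sections bear on the same data:

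- **Section 5.1 (flow chart).** The row "Survival Status" is marked once, in the Off-Study column. No later survival contact is listed.
- **Section 6.1.6.3.** The Off-Study visit "may be done earlier for patients embarking on additional anti-lymphoma therapy". Afterwards the section asks for disease status, with new therapy and progression among the points at which collection ends, and for details of any new anti-lymphoma treatment. It does not mention vital status.
- **Section 6.6.** "Exceptions to Serious Adverse Event Reporting include events related to progression of the cancer under study, including hospitalization or death".

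The Trial Summary gives 48 months of participation but attaches no survival contacts to it.

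**The concern.** Kaplan-Meier is valid for OS only if patients censored at a given time have the same later risk of death as those still under observation. Here the reason that required follow-up ends is progression itself. Section 3.1 describes a poor outlook for DLBCL patients who fail or cannot have transplant, which covers most of Arm B, so progression there marks a higher risk of death. For FL the same direction is an assumption, though a mild one.

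Censoring such patients soon after progression removes their later deaths and lets those still observed, who are mostly progression-free, stand in for them. The estimate then moves upward, and by more where more patients stop because of progression. Progression deaths are also exempt from SAE reporting, so the safety data would not supply them. The reported curve and its interval would show no sign of the problem, because the plan requires no later vital status for these patients.

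The gap does not affect every patient. Those who stop first for toxicity, CR, completion of therapy or (Arms A and B) less than PR without progression keep survival follow-up under Section 4.5.

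**Working it through.** The plan states no OS rate, OS precision or assumed hazard, so there is no figure of its own to reproduce. The check asks how far the Kaplan-Meier limit at 24 months would lie from true OS under stated assumptions.

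**Inputs from the documents.** Horizon 24 months (Section 2.2). Last required contact about 3 months after the last dose (Sections 4.5 and 6.1.6.3), taken here as 3 months after progression. Arm sizes 20, 17 and 25 (Trial Summary).

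**Assumed inputs.** Exponential PFS with hazard λ. A share d of first events are deaths. Exponential survival after progression with hazard μ. A share k of progressors keep survival follow-up regardless; the rest are censored 3 months after progression.

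**True OS.** With S(t) = exp(−λt):

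OS(24) = S(24) + (1 − d) · λ/(λ − μ) · [exp(−24μ) − exp(−24λ)]

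- DLBCL-like (median PFS 4 months, median survival after progression 8 months, d = 7.5%): exp(−24λ) = 2^(−6) = 0.0156, exp(−24μ) = 2^(−3) = 0.125, λ/(λ − μ) = 2. OS(24) = 0.0156 + 0.925 × 2 × 0.1094 = 0.218.
- FL-like (18 and 30 months, d = 10%): 2^(−4/3) = 0.397, 2^(−0.8) = 0.574, λ/(λ − μ) = 2.5. OS(24) = 0.397 + 0.90 × 2.5 × 0.1775 = 0.796.

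**Kaplan-Meier limit.** Let P(t) be the proportion alive after progression and still observed: the share k of all living progressors, plus the share 1 − k of those who progressed within the last 3 months. The observed death hazard is

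h(t) = [dλS(t) + μP(t)] / [S(t) + P(t)]

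and Kaplan-Meier converges to exp(−∫h) over 0 to 24 months. With k = 100% this returns the true value in every scenario.

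| Scenario | True OS | KM, k = 0% | k = 25% | k = 50% | k = 75% |
|---|---|---|---|---|---|
| DLBCL-like 4/8, d = 5-10% | 21-22% | 38-43% | 27-30% | 24-26% | 22-24% |
| Overstatement (points) | | 17-21 | 6-7 | about 3 | about 1 |
| FL-like 18/24 to 18/36, d = 5-10% | 77-84% | 86-92% | 83-89% | 81-87% | 79-85% |
| Overstatement (points) | | 6-11 | 4-7 | 3-4 | 1-2 |

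Simulation with 400,000 patients per scenario agrees: for DLBCL-like hazards with d = 7.5% and k = 0%, 40.6% against a true 21.8%.

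**Longer survival after progression in FL.** With median PFS 18 months and k = 0%, the overstatement is 3.5-4.7 points at a median of 60 months after progression, 2.1-3.2 at 84 months and 0.9-2.0 at 120 months.

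**A second model.** This one used a separate hazard of death without progression (3% per year) and censored all progressors at 3 months. With medians of 6 and 12 months it gave 67% against a true 42%; with 18 and 36 months, 90% against 83%. Bringing the last contact forward to 1 month after progression made the bias larger in every scenario.

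**Control.** With the same death hazard before and after progression, true OS was 48.6% and Kaplan-Meier 48.5%. The bias therefore comes from the link between progression and death, not from the amount of censoring.

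**Scale against sampling error.** With complete follow-up the 95% half-width in Arm B at OS near 21.5% is 1.96 × √(0.215 × 0.785 / 17) = 0.195, about 20 points. At OS of 80% it is about 18 points for 20 patients and 16 for 25.

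**The case against.** The loss of follow-up is partly inferred from silence. Section 4.5 names survival follow-up for one group but does not forbid it for progressors. Section 2.2 sets OS for each treatment group without excluding them. Section 6.1.6.3 sends everyone to routine surveillance and records later anti-lymphoma treatment, so some contact with progressors is planned. A single centre will learn of many deaths through its own records. If half of progressors are in fact followed, the modelled bias is about 3 points under DLBCL-like hazards, well inside an interval of ±20 points. The main FL range assumes a median of 24-36 months after progression; Section 3.1.1 puts median survival in advanced FL at over a decade, though not specifically after relapse. OS is descriptive and drives no decision.

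Most of this stands as a limit on size and severity. It does not remove the gap. None of these passages requires vital status after the Off-Study visit for a progressor, and the surveillance named in Section 6.1.6.3 concerns disease status. Capture through routine records may occur, but it is unplanned and could differ between arms. A wide interval shows imprecision to the reader; it does not show this bias.

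**Conclusion.** The concern holds. Followed as written, the plan makes required survival follow-up depend on progression, and Kaplan-Meier 2-year OS is then biased upward if progressors are censored at last contact.

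The direction rests on a higher risk of death after progression, which the protocol's background supports for DLBCL and which is assumed for FL. The size rests wholly on assumed hazards and on the unknown share of progressors whose deaths are captured anyway. It runs from about 1 point when most are captured to 17-21 points when none is, under DLBCL-like hazards. For FL with none captured it runs from about 1 to 11 points over the range of survival after progression examined. It matters most in Arm B if few progressors are followed.

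ORR, the two-stage designs, the safety stopping rules and, by this route, PFS are untouched. Because OS is a secondary descriptive endpoint with no decision rule, this should be fixed but does not threaten the trial's main conclusion.

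**What to change.** - **Sections 4.5, 5.1 and 6.1.6.3:** require vital status for every treated patient, by record review or telephone (for example every 3-6 months), to at least 24 months from first dose, regardless of progression, reason for stopping or new therapy.
- **Section 7.0:** define OS as time from first dose to death from any cause, censored at the date last known alive. Report how many patients in each arm are censored before 24 months, with the reason and progression status.

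The cost is an amendment to the wording and periodic status checks for at most 62 patients at one centre, with no added visits or procedures. The Trial Summary's 48-month duration less 24 months of enrolment leaves 48 − 24 = 24 months for the last patient enrolled. If the site already collects these data, the amendment only records the practice.
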